## LIST OF ABBREVIATIONS AND DEFINITION OF TERMS

Abbreviation	Term
AE	Adverse Event
ATC	Anatomical Therapeutic Chemical
BMI	Body Mass Index
CarerQoL-7D	Care-Related Quality of Life-7 Dimensions
CRF	Case Report Form
ECG	Electrocardiogram
FDA	United States Food and Drug Administration
ICH	International Conference on Harmonization of Technical Requirements for Registration of Pharmaceuticals for Human Use
MedDRA	Medical Dictionary for Regulatory Activities
NPMDS	Newcastle Pediatric Mitochondrial Disease Scale
PedsQL	Pediatric Quality of Life Inventory™
PT	Preferred Term
PTT	Partial Thromboplastin Time
QTc	corrected QT interval
SAE	Serious Adverse Event
SAP	Statistical Analysis Plan
SoA	Schedule of Assessments
SOC	System Organ Class
TEAE	Treatment Emergent Adverse Event
TFL	Table, Figure, and Listing
TID	ter in die (Three times a day)
WHO	World Health Organization

## 1. INTRODUCTION

The purpose of this statistical analysis plan (SAP) is to describe the procedures and the statistical methods that will be used to analyze data and report results for PTC743-CNS-005-LSEP (Protocol version 3.0 dated on 25 January 2023. De novo subjects are introduced in Protocol version 2.1 specific for France and Italy). Table, figure, and listing (TFL) specifications are contained in a separate document.

This SAP will be approved prior to the database lock.

### 1.1. Study Design

This is an open-label, Phase 3, safety study of vatiquinone in subjects with inherited mitochondrial disease who either participated in a previous clinical study or treatment plan (rollover subjects) or failed to meet study entry criteria in a prior vatiquinone clinical study (de novo subjects). A target of approximately 200 previously treated vatiquinone subjects and approximately 4 de novo subjects will be enrolled at up to approximately 40 investigational sites worldwide. De novo subjects will receive vatiquinone oral solution (100 mg/mL), up to 200 mg, administered orally or via feeding tube three times a day (TID). Rollover subjects will continue the dosing regimen from their parent study ([Figure 1](#)).

[figure not shown]
The study will include a Screening/Baseline Visit, a Treatment Period, and an End-of-Treatment Visit. For de novo subjects, the study visits will include Screening, Run-in, Baseline, Treatment Period and End-of-Treatment Visit. For subjects that will discontinue early, an Early Termination Visit will be performed 6 weeks after discontinuation.

The duration of vatiquinone treatment will be subject to the following conditions:

[figure not shown]
- The subject has the right to withdraw consent and discontinue vatiquinone at any time.
- The relevant regulatory authority and/or PTC Therapeutics (PTC) may discontinue the study at any time.
- If the subject's condition substantially worsens after initiating vatiquinone treatment in this study, the subject will be carefully evaluated by the investigator in consultation with the PTC medical monitor. The subject will be withdrawn from treatment if continuing would place the subject at risk.
- The investigator may withdraw the subject from vatiquinone treatment if, in the investigator's clinical judgment, it is not in the subject's best interest to continue.
- If the subject is unable to tolerate vatiquinone, the subject will be withdrawn from treatment.

Safety assessments for rollover subjects will be performed at Screening/Baseline and every 6 months. Safety assessments for de novo subjects will be performed at screening, baseline, months 1, 3, 6, and 12, and every 6 months thereafter. Safety assessments will also be collected for all subjects at the End-of-Treatment Visit. Detailed schedule of activities are described in [Table 2](#), [Table 3](#), and [Table 4](#). Diagrams of the study design are provided in [Figure 1](#), [Figure 2](#), and [Figure 3](#).

[figure not shown]
**Figure 1: Clinical Study Participation History of Subjects in Study PTC743-CNS-005-LSEP**

**Figure 2: Study Schema (Rollover Subjects)**

**Figure 3: Study Schema – De Novo Subjects (France/Italy)**

## 1.2. Study Objectives

### 1.2.1. Primary Objective

The primary objective of the study is to assess the safety of vatiquinone in subjects with inherited mitochondrial disease who participated in a previous vatiquinone clinical study or treatment plan, and de novo subjects who failed to meet study criteria in a prior vatiquinone clinical study.

### 1.2.2. Exploratory Objectives

Exploratory objectives of the study are:

- To explore the effects of vatiquinone in motor seizure count in subjects previously enrolled in Study PTC743-MIT-001-EP (referred to Study MIT-E hereafter) and in all de novo subjects.
- To explore the effects of vatiquinone based on the Newcastle Pediatric Mitochondrial Disease Scale (NPMDS) in subjects previously enrolled in Study MIT-E, and in all de novo subjects.
- To demonstrate the effects of vatiquinone on health-related quality of life in subjects previously enrolled in Study MIT-E, and in all de novo subjects.

### **1.3. Endpoints**

#### **1.3.1. Primary Endpoints**

The primary endpoints of the study are adverse events (AEs), serious AEs (SAEs), electrocardiogram (ECGs), vital signs, and laboratory data (hematology, biochemistry, and urine data).

#### **1.3.2. Exploratory Endpoints**

Exploratory endpoints of the study are as follows:

- Total frequency of motor seizures per 28 days.
- Change in the total score for NPMDS Sections 1 to 3.
- Measured by the CarerQoL-7D and Pediatric Quality of Life Inventory™ [PedsQL] questionnaires.

### **1.4. Sample Size Determination**

The sample size for this study is based on the number of subjects in previous vatiquinone studies and is not based upon any formal statistical hypothesis.

## **2. STUDY POPULATIONS**

Safety population includes all subjects who receive at least 1 dose of vatiquinone in the study. Safety population will be used for all summaries in this study.

## **3. GENERAL CONSIDERATIONS**

For continuous variables, mean, standard deviation, median, minimum, maximum, and number of subjects with non-missing data will be provided. For categorical variables, the number and percentage of subjects in each category will be provided.

Day 1 is defined as the first dose date. Study days after day 1 are calculated as: assessment date - first dose date + 1. Study days prior to day 1 are calculated as assessment date - first dose day.

Measurements collected from unscheduled visits, or repeated assessments will be included in the listings only, unless otherwise specified.

The descriptive summaries will be presented by total subjects for safety endpoints. Exploratory and efficacy endpoints will be presented in listings only. All summaries will be based on nominal visits.

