## 5. PRIMARY ANALYSES

All primary analysis will be based on the safety population. Descriptive summaries will be based on nominal visits.

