#### 5.1.1. Treatment Emergent Adverse Event

A TEAE is defined as an AE that had an onset date on or after the first dose of study drug but prior to 30 days after last dose or it occurs prior to first dose of study drug and worsens in severity after first dose of study drug.

AEs with missing or partial onset date and cannot be determined if it occurred prior to the first dose of study treatment will be counted as TEAEs.

An overview TEAE table, including number and percentage of subjects with TEAEs, TEAEs by maximum CTCAE grade, treatment related TEAE, treatment related TEAE by maximum CTCAE grade, treatment-emergent SAEs (TESAEs), treatment related TESAEs, and TEAEs leading to study discontinuation will be provided.

Summary information (the number and percentage of subjects) will be tabulated for:

- Incidence of TEAEs by SOC and PT
- Incidence of TEAEs by PT in descending order
- Incidence of treatment-related TEAEs by SOC and PT
- Incidence of TEAEs by SOC, PT, and maximum CTCAE grade
- Incidence of TEAEs by SOC, PT, and relationship to study drug

TEAE tables will be sorted by SOC and then PT in decreasing frequency of the number and percentage of subjects in total column.

A by-subject data listing will be provided for all AEs.

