## 5.2. Clinical Laboratory Parameters

Laboratory parameters (Table 1) values and the change from baseline will be summarized for each visit.

A by-subject listing of laboratory results will be provided for hematology, coagulation, biochemistry, and urinalysis respectively.

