## 5.3. Vital Signs

Vital signs (temperature, respiratory rate, systolic blood pressure, diastolic blood pressure, heart rate, oxygen saturation, weight, and BMI) and the change from baseline will be summarized for each visit.

A by-subject level listing of vital signs will be provided.

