## 5.4. Electrocardiogram (ECG)

ECG results and the change from baseline (heart rate, PR interval, RR interval, QRS interval, QTc interval) along with ECG interpretations will be summarized for each visit.

A subject data listing of ECG results will be generated.

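### Post-baseline laboratory, vital-sign and ECG excursions first seen at an unscheduled or repeat test enter no table for these primary endpoints, because SAP sections 5.2 to 5.4 make no exception to the listings-only rule

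*SAP*

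**What the plan says.** SAP section 1.3.1 names as primary endpoints, beside AEs and SAEs, "electrocardiogram (ECGs), vital signs, and laboratory data (hematology, biochemistry, and urine data".

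Section 3 (General Considerations) sets two rules for all outputs: "Measurements collected from unscheduled visits, or repeated assessments will be included in the listings only, unless otherwise specified", and "All summaries will be based on nominal visits". Section 5 repeats the second for the primary analyses: "Descriptive summaries will be based on nominal visits".

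The three sections on these endpoints then plan the following tables:

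- 5.2, laboratory: "Laboratory parameters (Table 1) values and the change from baseline will be summarized for each visit".
- 5.3, vital signs: the listed measurements, ending "oxygen saturation, weight, and BMI) and the change from baseline will be summarized for each visit".
- 5.4, ECG: intervals and their change from baseline, "along with ECG interpretations will be summarized for each visit".

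Each section adds a listing. Sections 1 and 7 place the table, figure and listing specifications in a separate document.

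**The concern.** Keeping off-schedule values out of by-visit tables is ordinary practice, because they do not belong to any visit column. It is normally accompanied by a per-subject summary, such as worst value, shift from baseline or threshold category, that takes in every post-baseline result. Here no such summary is planned, so the listings-only rule has nothing to balance it.

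Unscheduled tests are often ordered because of symptoms or an earlier result, so they are the ones more likely to show a marked value. The study has no formal hypothesis and its safety tables are descriptive, so those tables are the primary result. If they leave such values out by rule, they can understate how many subjects had a marked excursion on treatment, and a reader would have to work the count out from the listings.

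**Working it through.** The SAP gives no figure on this point to reproduce, so the check is textual: does any section supply the exception that section 3 allows for?

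1. **Search for an exception.** Sections 5, 5.2, 5.3 and 5.4 and the laboratory parameter table (Table 1) contain none. Section 5 reinforces the nominal-visit rule. Sections 5.2 to 5.4 each plan summaries by visit and contain no worst post-baseline, shift or threshold summary.

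2. **What the rule does, case by case.**
 - *Scheduled value abnormal, repeat normal or no worse.* The scheduled value stays in the by-visit table and the repeat is listed. The excursion is not hidden.
 - *Scheduled value abnormal, repeat worse.* The scheduled value is tabulated. The worse value is in the listing only.
 - *Scheduled values unremarkable, unscheduled value abnormal, resolved by the next scheduled visit.* No laboratory, vital-sign or ECG table shows it. It is in the listing, and in the TEAE tables if reported as an AE with onset "on or after the first dose of study drug but prior to 30 days after last dose".
 - *Unscheduled value abnormal and still abnormal at the next scheduled visit.* The later value is tabulated. The first is listed.

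 The gap therefore concerns excursions, or their worst extent, seen only at an unscheduled or repeat test.

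3. **Where scheduled tests fall.** Appendix 1, Table 2 sets rollover on-site visits every 6 months (168±7 days). Footnote d limits the 3-monthly contact between them to AEs, weight and concomitant medications. Apart from End-of-Treatment and Early Termination Visits, which are themselves scheduled, a laboratory, ECG or vital-sign test other than weight done between on-site visits is off schedule. De novo subjects have earlier visits in the first year and follow Table 2 after Month 12.

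4. **What the planned tables can show.** Section 3 requires minimum and maximum for continuous variables, so an extreme scheduled value is visible at its visit, and ECG interpretations are tabulated by visit. Neither tells how many different subjects were ever abnormal: the same subject may account for the extreme at several visits, and per-visit counts cannot be added across visits.

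5. **Size.** A calculation would need the rate of unscheduled and repeat tests and the rate of abnormal results at them. The SAP gives neither.

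**The case against.** The strongest reply is that nothing here is wrong or contradictory. Sections 3 and 5 to 5.4 agree with one another, every result is listed, AEs are themselves a primary endpoint and are tabulated by maximum CTCAE grade, and the by-visit tables carry minimum, maximum and ECG interpretations. In an open-label study without a comparator, worst-value counts also depend on how often each subject was tested.

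Most of that stands. It makes this an improvement to a stated rule, not an error. It does not close the gap: AE tables capture an excursion only if it is reported as an AE, section 1.3.1 names these measurements as endpoints in their own right, and a listing gives no count.

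Four stronger readings are tempting and are not supported:

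- *That confirmatory repeats as such cause understatement.* A repeat that only confirms a scheduled abnormal value leaves that value in the table.
- *That the final outputs will certainly lack such a summary.* The separate specifications are not available and could contain one. The claim is about the SAP text, which is where an exception to its own general rule belongs.
- *That visit spacing, or the share of subjects on the rollover schedule, measures the understatement.* They show only where the rule applies.
- *That section 3 conflicts with the baseline definition in 3.1.* Section 3.1 can reasonably be read as the specific rule for baseline. That is a separate matter and not part of this point.

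**Conclusion.** The point holds in a limited form. Under the SAP as written, a post-baseline excursion first seen at an unscheduled or repeat test enters no laboratory, vital-sign or ECG table, and no planned output for these endpoints gives the number of subjects ever abnormal. No data are lost, and there is partial coverage through listings, TEAE tables, per-visit extremes and by-visit ECG interpretations. The size of any understatement is unknown and cannot be derived from the SAP. The conclusion rests on two things: that the SAP text governs, since the table specifications were not available, and that tests between scheduled visits are recorded as unscheduled. It is a cheap improvement that should be made, because it concerns primary endpoints with scheduled tests about 6 months apart for rollover subjects.

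**What to change.** Leave the by-visit tables on nominal visits. Add to sections 5.2 to 5.4, as a named exception to sections 3 and 5, a per-subject worst post-baseline summary that includes unscheduled and repeat results:

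- **Laboratory:** shift from baseline to worst value, by normal range or by CTCAE grade where one is defined.
- **ECG:** number and percentage of subjects by category of worst QTc and of worst QTc change from baseline.
- **Vital signs:** number and percentage of subjects by high and low category. The categories should be age-appropriate, since the study uses paediatric instruments.

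Fix the categories before database lock. State the window, for example the TEAE window in 5.1.1, with later results shown separately. That window is a suggestion: the SAP sets none for these data.

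The cost is SAP wording and a few standard tables from data already collected and listed. The drawback is that worst-value counts depend partly on testing frequency. Say so in a footnote, and show the number of subjects with any unscheduled or repeat result beside each summary.

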### **3.1. Baseline**

For safety and efficacy endpoints, baseline will be defined as the last measurement prior to or on the date of first dose date in PTC743-CNS-005-LSEP.

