## APPENDIX 1. SCHEDULE OF EVENTS

**Table 2:** Schedule of Assessments – Rollover Subjects

Study Period	Screening/Baseline a	Treatment		EOT Visit	ET (6 Weeks After D/C) b
Study Month	Day 1	Telephone Visits 3 Months (84±7 Days) After On-Site Visits	Every 6 Months (168±7 Days)		
Informed consent	X c				
Demographics	X				
Medical history	X				
Vital signs	X		X	X	X
Height	X				
Weight	X	X d	X	X	X
Physical examination	X		X	X	X
12-Lead ECG	X		X	X	X
Urine pregnancy test (WOCBP) l	X		X	X e	X
Hematology (CBC w/ differential)	X m		X m	X m	X m
Serum chemistry	X m		X m	X m	X m
Coagulation panel	X m		X m	X m	X m
Urinalysis f	X		X	X	X
NPMDS g	X		X	X	X
CarerQoL-7D g	X h		X	X	X
PedsQL g	X h		X	X	X
Drug dispensed i	X	X	X		
Pre-/post-shipment contact j		X			
Drug compliance k			X	X	X
AE/SAE assessment	X	X d	X	X	X
Prior/concomitant medication	X	X d	X	X	X

**Abbreviations:** AE, adverse event; CBC, complete blood count; D/C, discontinuation; ECG, electrocardiogram; EOT, End-of-Treatment; ET, Early Termination; NPMDS, Newcastle Pediatric Mitochondrial Disease Scale; PedsQL, Pediatric Quality of Life Inventory™; SAE, serious adverse event; Study MIT-E, Study PTC743-MIT-001-EP; WOCBP, women of childbearing potential

a On-site visit applicable to all subjects rolling over to this study. For subjects rolling over from Study MIT-E, the Screening/Baseline Visit in this study will also be the Week 72 visit in Study MIT-E.

b Subjects who discontinue vatiquinone prematurely should complete an ET Visit.

c Informed consent will be signed before any study procedures. In case the subject/caregivers cannot attend the Screening/Baseline Visit in the clinic, remote consenting can be obtained.

d Clinical site staff will contact subject or parent(s)/legal guardian(s) every 3 months (by telephone if there is no clinic visit) to assess AEs, weight, and concomitant medications.

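### Safety summaries are planned for all subjects combined, so de novo adverse events get no separate summary and the by-visit totals change cohort between rows

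*SAP*

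**What the plan says.** SAP section 3 states that "The descriptive summaries will be presented by total subjects for safety endpoints", and also that "All summaries will be based on nominal visits". Section 2 defines one safety population and uses it throughout. Section 5.1.1 orders the TEAE tables by a total column. Sections 5.2 to 5.4 summarize laboratory, vital-sign and ECG values and their changes at each visit. None of these sections calls for a split by cohort.

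The primary objective (section 1.2.1) covers subjects from earlier vatiquinone studies or treatment plans "and de novo subjects who failed to meet study criteria in a prior vatiquinone clinical study". On numbers, section 1.1 says: "A target of approximately 200 previously treated vatiquinone subjects and approximately 4 de novo subjects will be enrolled".

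The schedules differ. Section 1.1 says of the first group, "Safety assessments for rollover subjects will be performed at Screening/Baseline and every 6 months", and of the second, "Safety assessments for de novo subjects will be performed at screening, baseline, months 1, 3, 6, and 12, and every 6 months thereafter". For both, section 3.1 says "baseline will be defined as the last measurement prior to or on the date of first dose date in PTC743-CNS-005-LSEP". Footnote a to Table 2 in Appendix 1 adds: "For subjects rolling over from Study MIT-E, the Screening/Baseline Visit in this study will also be the Week 72 visit in Study MIT-E".

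**The concern.** The SAP keeps the two groups apart in its objective, dosing description and visit schedules, but merges them in the primary analysis. Two things are lost.

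First, a group named in the primary objective has no adverse event summary of its own. An event in one de novo subject adds the same single count to the total column as an event in one rollover subject, although it is a quarter of one group and 0.5% of the other.

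Second, consecutive rows of a by-visit table are read as one series. Here the early rows describe newly treated subjects and the later rows almost entirely previously treated ones. A mean change could seem to fade only because different people are being averaged. Where both groups share a row, the change is also measured from two kinds of starting point.

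**Working it through.** The SAP states no power or precision figure for safety, and section 1.4 says the sample size rests on no formal hypothesis, so there is no planned figure to reproduce. The inputs are the enrolment targets in section 1.1: 200 rollover, 4 de novo, 204 in all.

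**Shares.** Rollover 200/204 = 98.0%; de novo 4/204 = 2.0%.

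**Adverse events confined to de novo subjects (0 of 200 rollover).**

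| De novo subjects with the event | Share of de novo group | Total column |
|---|---|---|
| 1 of 4 | 25% | 1/204 = 0.5% |
| 2 of 4 | 50% | 2/204 = 1.0% |
| 4 of 4 | 100% | 4/204 = 2.0% |

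The last row is what would also be printed for 4 of 200 rollover subjects and no de novo subject.

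**Largest effect on the total.** Total rate minus rollover rate = (4/204) × (de novo rate − rollover rate), so the difference is at most 4/204 = 2.0 percentage points. If 100 of 200 rollover subjects have the event (50.0%), the total lies between 100/204 = 49.0% and 104/204 = 51.0%.

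**Who is in each by-visit row, from section 1.1 and Appendix 1.**
- Month 1: de novo only, about 4.
- Month 3: de novo only, about 4, except weight and so possibly BMI. Rollover subjects report weight at the 3-monthly telephone contact (Table 2, footnote d).
- Month 6: shared according to section 1.1, but the de novo column headers in the available text of Appendix 1 do not settle it.
- After Month 12: clearly shared, because de novo subjects then follow the rollover schedule (footnote b to Tables 3 and 4). Up to about 204.

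**What that does to a series of means.** For illustration only, assume a constant mean change of d units in de novo subjects and 0 in rollover subjects. Months 1 and 3 print d × 4/4 = d. A shared visit prints d × 4/(4 + number of rollover subjects attending).

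| d (assumed) | Months 1 and 3 | Shared visit, 200 rollover | Shared visit, 100 rollover |
|---|---|---|---|
| 10 | 10 | 0.20 | 0.38 |
| 20 | 20 | 0.39 | 0.77 |
| 40 | 40 | 0.78 | 1.54 |

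The printed mean falls by 98.0% (1 − 4/204) or 96.2% (1 − 4/104) with no subject changing. The percentage fall is fixed by the shares and does not depend on d.

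**Baseline.** For rollover subjects, who section 1.1 says continue their parent-study regimen, the value at first dose in this study generally follows earlier vatiquinone; for those from Study MIT-E it is taken at that study's Week 72 visit. For de novo subjects it generally precedes treatment.

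**What a de novo column could support.** With 0 events in 4, the one-sided 95% upper limit is 1 − 0.05^(1/4) = 52.7%. The column can describe and no more.

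**The case against.** Pooling is stated openly, and the study is descriptive throughout. The objective can be read as one question about both groups together, with no comparison requested. Section 3.3 records only the exploratory endpoints as departing from the protocol, so nothing suggests that total-only safety tables break a commitment. De novo subjects are in every adverse event total. By-subject listings are planned for adverse events, deaths, SAEs, discontinuations, laboratory results, vital signs, ECG and physical examination, and four subjects can be read one by one. Section 3 also prints the non-missing count, minimum and maximum with each continuous summary, so a drop to about 4 is visible. The table shells are a separate document and may already identify cohort.

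Most of this stands and limits the point. It does not remove it. A count of 4 does not tell the reader that these are newly treated subjects or that baseline means something else for them, and a maximum is not attributed to a cohort. The SAP text does not say that the listings carry cohort. Small numbers rule out inference, but they are no reason to average unlike groups in a descriptive study.

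A reader might infer that de novo subjects are left out of the adverse event analysis, that pooling distorts the overall safety result, or that the SAP contradicts its objective. The documents support none of these: the subjects are counted, the shift is at most about 2 points, and the objective does not expressly ask for separate estimates.

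**Conclusion.** The point holds as a modest weakness of presentation that should be corrected. As written, the SAP gives no separate adverse event summary for a group its primary objective names, and it yields by-visit totals whose adjacent rows cannot be compared. The effect on an adverse event percentage is at most about 2 percentage points, and the conclusion on rollover subjects does not change.

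This rests on the enrolment targets being roughly met, on the section 1.1 schedule, and on the SAP text alone, since the shells are not at hand. The 10, 20 and 40 unit changes are assumed and show only the mechanism; they are not evidence that any parameter will behave this way. Sharing of rows is certain after Month 12; at Month 6 it depends on section 1.1.

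**What to change.** In section 3, replace the total-only sentence with:
- Rollover, De novo and Total columns for the TEAE tables.
- By-visit laboratory, vital-sign and ECG values and changes from baseline presented by cohort.
- A label stating that the rollover change is change from entry to this study, after earlier vatiquinone treatment.
- A statement that the de novo column is descriptive only and that no inference will be drawn from it.
- A requirement that the by-subject listings identify each subject's cohort, if the shells do not already do so.

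This needs SAP wording and matching shells only, using data already collected. The downside is wider tables and a descriptive column of about 4 subjects.
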